Specific Aim 2. To compare rates of initiation of hypertensive therapies in women randomized to the study drug compared to those randomized to placebo. We hypothesize that women randomized to the study drug will be less likely to be initiated on hypertensive therapies between delivery and 6 weeks postpartum.

Specific Aim 3. To compare rates of severe maternal morbidity in women randomized to the study drug compared to those randomized to placebo from the time of discharge to 6 weeks postpartum. We hypothesize that women randomized to the study drug will have lower rates of severe maternal morbidity between delivery and 6 weeks postpartum compared to those randomized to placebo.

- **Sub-aim 1: To compare hypertensive-related unscheduled presentations between those who have been randomized to the study drug and those randomized to placebo.** We hypothesize that women randomized to the study drug will have fewer triage and emergency department visits for hypertension-related complaints episodes after discharge.
- **Sub-aim 2: To assess adverse effects of therapy in the study group and the control group.** We hypothesize that there will be no difference in adverse effects, such as discontinuation of breastfeeding, hypotension, and electrolyte abnormalities in women randomized to the study drug compared to those randomized to placebo.
- **Sub-aim 3: To analyze factors associated with incidence of severe maternal morbidity in the study group and the control group.** We hypothesize that factors such as racial and ethnic identity and age will be associated with increased incidence of severe maternal morbidity.

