2. **Adherence.** For both groups, proportion of medication course completed will be recorded
3. **Time to initiation of medications.** For both groups, time to initiation of anti-hypertensive medications will be tracked
4. **Final plan at 6 weeks.** For both groups, continuing medication regimens at 6 weeks will be collected.
5. **Hospital readmissions.** Hospital readmission for any indication will be collected for both groups
6. **Triage/ED visits.** Presentation to the obstetric triage unit or the emergency department for any indication will be collected for both groups
7. **Maternal morbidity and mortality.** Incidences of eclampsia, stroke, PRES, maternal death will be collected for both groups
8. **Breastfeeding continuation.** Rates of breastfeeding continuation will be collected for both groups
9. **Adverse effects.** Incidences of hypotension, electrolyte abnormalities, and development of renal insufficiency will be collected for both groups.

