2.4 Statistical Analyses

2.4.1 Sample size and statistical power

A case-control study of women who were normotensive at delivery but who were later hospitalized with a diagnosis of severe preeclampsia compared to women who remained normotensive in the postpartum period and women who were diagnosed with preeclampsia in the antenatal period determined that differences in mean arterial blood pressure could be detected following delivery. This retrospective review determined that women who developed de novo postpartum preeclampsia had a greater increase in MAP after delivery than normotensive women (5.0 ± 6.4 mm Hg vs 0.2 ± 6.0 mm Hg, $p < 0.004$).¹³ Though data is scarce on whether a change in MAP can be detected in women with a broader diagnosis of de novo postpartum hypertension, using this reference data to assign an effect size of 5 mm Hg with standard deviation of 6.4 mm Hg and a baseline MAP of 83 mm Hg will provide a conservative estimate of a clinically meaningful change. For a power of 90%, a significance level 5%, and anticipated post-randomization losses of 10%, 41 patients will be needed for each group, or 82 patients total.

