2.4.2 Statistical analysis

For analysis of discrete (categorical) data in independent samples, the Chi-squared test or Fisher exact probability test will be utilized. For group comparisons, continuous data that satisfy the assumptions of normality and homoscedasticity (homogeneity of variance) will be analyzed by t-test (for 2 independent samples) or analysis of variance (>2 groups, ANOVA) with post hoc comparisons by Scheffe tests. When possible, continuous data that do not fulfill the aforementioned assumptions will be mathematically transformed (e.g., logarithmic transformation) before performing t-tests or ANOVA. In some cases, data that do not satisfy these assumptions will be analyzed by nonparametric methods [Mann-Whitney U Test (for two independent samples) or Kruskal-Wallis One-Way ANOVA (for more than two independent samples)]. Significant Kruskal-Wallis ANOVAs will be followed by Dunn tests for post hoc analysis. The degree of linear association between variables will be measured by the Pearson product moment correlation coefficient or the Spearman rank-order correlation coefficient and their corresponding tests of significance. Multivariate linear or logistic regression will be utilized where appropriate. In all cases, statistical significance will be assumed when $p < 0.05$. Propensity score analysis will be used as a balancing score as deemed necessary.

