2.5. Anticipated outcomes

The primary outcome will be the difference in the mean arterial blood pressure in the 24 hours prior to discharge or antihypertensive therapy initiation (whichever occurs first) between patients in the study drug group and those in the placebo group. We anticipate that the patients randomized to the study drug will have a significantly lower mean arterial blood pressures than those randomized to placebo. We propose that this will lead to faster normalization of blood pressures, reduce the rate of development of de novo hypertension, specifically preeclampsia, and reduce the morbidity and mortality associated with de novo postpartum hypertension without adverse effect.

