2.10 Risks, Benefits, and Monitoring

2.10.1 Risks

Lasix (furosemide) is in a class of drugs call diuretics and is commonly used to treat edema (swelling) and hypertension. Lasix is considered safe for use in adults and pediatric patients. If given in excessive amounts, Lasix can cause dehydration and electrolyte imbalances. Other possible side effects include dryness of mouth, thirst, weakness, lethargy, drowsiness, restlessness, muscle pains or cramps, muscular fatigue, hypotension, oliguria, tachycardia, arrhythmia, or gastrointestinal disturbances such as nausea and vomiting. Increases in blood glucose and alterations in glucose tolerance tests (with abnormalities of the fasting and 2-hour postprandial sugar) have been observed, and rarely, precipitation of diabetes mellitus has been reported.

In patients with severe symptoms of urinary retention (because of bladder emptying disorders, prostatic hyperplasia, urethral narrowing), the administration of furosemide can cause acute urinary retention related to increased production and retention of urine. Thus, these patients require careful monitoring, especially during the initial stages of treatment.

Lasix is contraindicated in patients with anuria and in patients with a history of hypersensitivity to furosemide. Therefore, if you do not produce urine or if you have ever had an allergic reaction to furosemide, you will not be able to participate in the study.

A very small amount of Lasix may pass to the baby through breast milk. Lasix may also inhibit lactation.

Since the use of the study drug is investigational, there may be other risks that are unknown. These may be minor or severe. They may find out new risks while the study is going on. If this happens, the research staff will tell the participants any new information, whether it may affect her, and what, if anything, to expect.

Another risk of taking part in this study is the possibility of a loss of confidentiality. All efforts will be made to maintain confidentiality, including storage of data on secure servers and deidentification of data after it is collected.

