The Principal Investigator and Lead Co-Investigator will also be responsible for monitoring the trial, starting at the point the patient begins the study drug in the hospital, the day of delivery. The patient will be given the research team contact information on the consent and instructed to report any concerns about or adverse effects from the study drug (Lasix/furosemide or placebo). Of course, in the case of any medical emergency, the patient will be cautioned to call 911. The medical members of the research team will make the determination of relationship of each adverse effect to the Lasix (furosemide). During the study, the Principal Investigator or study site personnel will be responsible for querying and recording adverse events and serious adverse events. All adverse events – regardless of seriousness or relationship to the study drug – occurring from the signature of informed consent through the period of study drug intake (within eight hours after delivery up to 5 days after delivery), should be recorded.

The research team will be keeping track of the patient's progress while she is recovering post-delivery, including blood pressures, labs, and post-procedural complications. If the patient develops any significant hypokalemia or severe renal dysfunction, which will be reflective in her labs, she will discontinue the drug. When the patient returns for her routine follow-up visit around 2 weeks and 6 weeks, the research team will follow up her postpartum course and monitor for any adverse events. If the patient is readmitted prior to her research follow-up visit, the research team will be notified by her clinical providers. The total monitoring period will last 6 weeks from the time of delivery. The entire clinical trial will be stopped if there is greater than expected morbidity from the study drug – that is, if multiple patients have to withdraw from the trial due to adverse effects from the Lasix (furosemide).

Once a mild adverse event is noted, the Principal Investigator will be notified by email within 1 to 2 days. If a moderate or serious adverse event or unanticipated problem arises involving risk to subjects or others, the Principal Investigator will be notified immediately by email. This information will then be relayed by the Principal Investigator to the appropriate monitoring and

regulatory entities, if needed. However, this is a minimal-risk study and such events are anticipated to occur very rarely.

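### The safety sub-aim hypothesises no difference in adverse effects, but the plan has only tests of difference at 41 per arm, so a non-significant result cannot support it

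*Combined protocol and SAP*

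**What the plan says.** Section 2.2, Specific Aim 3, Sub-aim 2, sets out to assess adverse effects in both groups and adds: "We hypothesize that there will be no difference in adverse effects, such as discontinuation of breastfeeding, hypotension, and electrolyte abnormalities". Section 2.5 anticipates that treatment will "reduce the morbidity and mortality associated with de novo postpartum hypertension without adverse effect".

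The methods for binary data are in section 2.4.2: "For analysis of discrete (categorical) data in independent samples, the Chi-squared test or Fisher exact probability test will be utilized", and "Multivariate linear or logistic regression will be utilized where appropriate". One significance rule, p < 0.05, covers every analysis. The documents contain no equivalence or non-inferiority margin, no confidence-interval criterion and no expected adverse-effect rate. They do not say how a non-significant safety comparison will be read.

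Section 2.4.1 bases the sample size on MAP: "41 patients will be needed for each group, or 82 patients total", including 10% losses.

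On the harms themselves, section 2.10.1 warns that "Lasix may also inhibit lactation". Section 2.3.7 says "Incidences of hypotension, electrolyte abnormalities, and development of renal insufficiency will be collected for both groups". Section 2.10.4 makes study staff responsible for "querying and recording adverse events and serious adverse events" and provides for review by a data safety monitoring board (DSMB).

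**The concern.** For the other between-arm hypotheses in section 2.2, the investigators expect furosemide to do better, so rejecting the null supports the claim. In this sub-aim the claim is the null. A test of difference can contradict it but cannot establish it: p > 0.05 fits both no excess and a substantial excess that a small trial missed.

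The hypothesis also covers an effect for which the protocol gives a reason to expect a difference. Breastfeeding discontinuation is the first effect named, and the risk section says the drug may inhibit lactation. The drug is to be given preventively to women with no antenatal hypertension diagnosis, and section 2.6 says the data are meant to inform future guidelines. A reader of the results could take a row of non-significant p-values as confirming the stated hypothesis when the data would not justify that.

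**Working it through.** **1. The plan's own sample size.** Inputs from 2.4.1: difference 5 mm Hg, SD 6.4 mm Hg, power 90%, significance level 5% (two-sided assumed), losses 10%.

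n per arm = 2 × (1.960 + 1.282)² × 6.4² / 5² = 34.4, so 35. Then 35 / 0.9 = 38.9, so 39. The t-distribution version gives 36, and 36 / 0.9 = 40. The stated 41 is within two patients of both. The size is sound for MAP, and adverse effects play no part in it.

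**2. Power of the planned tests for adverse effects.** The documents give no rates, so all rates here are assumptions, shown as a range. Method: two independent binomials with n = 41 per arm. Power is the sum of Pr(X = i) × Pr(Y = j) over all tables (i, j) with two-sided p < 0.05, enumerated exactly.

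| Assumed true rates, furosemide v placebo | Fisher | Chi-squared, uncorrected |
|---|---|---|
| 10% v 5% | 4.5% | 15% |
| 15% v 5% | 19% | 36% |
| 20% v 5% | 43% | 59% |
| 25% v 5% | 66% | 77% |
| 30% v 5% | 83% | 90% |
| 20% v 10% | 17% | 25% |
| Breastfeeding discontinuation 30% v 20% | 13% | 18% |
| Breastfeeding discontinuation 35% v 20% | 25% | 33% |
| Breastfeeding discontinuation 40% v 20% | 42% | 51% |

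With the planned 10% losses, 41 × 0.9 = 36.9, or about 37 per arm. Power is then 16% / 33% for 15% v 5% and 78% / 86% for 30% v 5%.

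**3. What an interval shows and a p-value hides.** Suppose 6/41 v 2/41 are observed, a three-fold excess. The difference is 14.6% − 4.9% = 9.8 points (4/41). Fisher gives p = 0.26 and chi-squared p = 0.14, so the result is not significant.

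The Newcombe interval uses the Wilson limits (l, u) for each arm: 6.9% to 28.4% for 6/41 and 1.3% to 16.1% for 2/41.

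- Lower limit: 9.8 − √[(14.6 − 6.9)² + (16.1 − 4.9)²] = −3.9 points.
- Upper limit: 9.8 + √[(28.4 − 14.6)² + (4.9 − 1.3)²] = +24.0 points.

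These limits use unrounded inputs. The data would be compatible with an excess of up to 24 points.

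With 0/41 in both arms, each Wilson upper limit is 8.6%, so the interval is −8.6 to +8.6 points. Even no events at all would not show equality.

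**4. Could a margin rescue the hypothesis?** Take non-inferiority, one-sided 2.5%, and equal true rates p. Power at 41 per arm to exclude an excess of m is Φ(m / √[2p(1 − p)/41] − 1.96). For m = 10 points this is 55% at p = 5%, 33% at 10%, 20% at 20% and 17% at 30%. Of the margins tried (5, 10 and 15 points), only 15 points at a 5% rate reaches 80% (88%). Estimation is therefore the realistic course at this size.

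**The case against.** The strongest reply is that the documents never make the faulty inference. The operative verb in the sub-aim is to assess, and the no-difference statement can be read as an expectation. Section 2.5 is a forecast, not an analysis rule. A reader might infer that the investigators plan to report p > 0.05 as proof of safety, but no section says so. What stands against the reply is that the sentence is framed like the testable hypotheses around it, falls under the same p < 0.05 rule, and is given no other route to confirmation.

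A second reply is that low power for uncommon harms is normal in a trial of 82 women sized on a continuous outcome, and that this is one secondary sub-aim. That is correct and limits the weight of the point. It is a reason not to frame the sub-aim as a hypothesis of no difference.

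A third is that participants are protected. The DSMB meets at 25%, 50% and 75% enrolment, adverse events are recorded, the drug is stopped for significant hypokalaemia or severe renal dysfunction, and there is a trial stopping rule. This stands, and nothing here suggests a gap in participant protection. These measures do not turn a null comparison into evidence of no difference.

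Finally, the rates are assumed, and large excesses would probably be detected. A reader might infer that the trial cannot detect any harm, and the 30% v 5% row shows otherwise.

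**Conclusion.** The concern holds in a limited form: the plan states a hypothesis of no difference that its own methods cannot support, whatever the data. Across the assumed ranges, a two- to three-fold increase from 5%, or a rise of 10 to 15 points in breastfeeding discontinuation from 20%, would more likely than not be non-significant with either planned test. An increase from 5% to 30% would probably be found.

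These figures rest on assumed event rates, two-sided testing, and outcome data on all 41 women per arm; losses reduce the power further. The primary MAP analysis and the sample size are not affected.

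A reader might also infer that the safety conclusion matters as much as the MAP result. The documents do not say so: MAP is primary, and 2.6 describes the goal as collecting data for later guidance. The change is worth making because it alters what the trial may conclude about safety at very little cost.

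**What to change.** - **2.2, Aim 3, Sub-aim 2:** reword as estimating the difference in adverse effects between arms, and remove the no-difference hypothesis.
- **2.4.2:** report each adverse effect by arm as a risk difference with a 95% confidence interval (for example Newcombe). State that a non-significant test will not be read as absence of harm.
- **Denominators, by outcome:**
  - hypotension: women with inpatient or home blood pressure readings;
  - breastfeeding discontinuation: women who started breastfeeding and have survey data;
  - electrolyte and renal events: women tested, labelled as clinically detected and reported descriptively with the number tested per arm.

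  Using all randomised women throughout would count untested or unsurveyed women as event-free and pull the difference towards zero.
- **2.5:** drop the forecast of benefit without adverse effect.

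**Cost.** No extra patients, visits or procedures. It needs text and table changes and a little chart abstraction, because whether each woman had electrolytes or creatinine tested is not a listed item in 2.3.7. The intervals will be wide, and the trial gives up a no-difference safety statement. The documents do not schedule these laboratory tests; that is a separate matter which this change does not resolve.

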2.3 Methods

2.3.1 Study Design

This will be a randomized control trial, in which women who are at high risk of developing de novo postpartum hypertension will be assigned to either a five-day course of PO furosemide 20 mg daily or a five-day course of PO placebo after delivery.

Patients will be informed of the study in the antenatal period, within four weeks of their estimated date of delivery or on admission to labor and delivery and will be deemed eligible, enrolled and randomized from the postpartum service within 8 hours after delivery.

Randomization will be performed by the Columbia Research Pharmacy, and the study drug or placebo will be dispensed to the postpartum floor to be administered by the patient's assigned postpartum nurse. Blood pressure measurements will occur every six hours (or more if clinically indicated) until the time of discharge. Upon discharge, the remainder of the five-day course of the study drug or placebo will be dispensed to the patient to complete. Patients in both groups will be asked to check their blood pressure twice per day, once in the morning and once in the evening, and will receive text message reminders twice a week. In order to check their blood pressures after discharge, patients in both groups will be given a Philips Bluetooth-enabled blood pressure cuff, which will transmit blood pressure measurements via Bluetooth from the monitor to the eCC. These patients will be educated on the use of and enrolled in the software by research investigators who have been in-serviced on the devices prior to discharge. The tablets are cellular-enabled, so no wireless connection is needed in the patient's home. Criteria for contacting their provider will be reviewed with and provided in writing to the patients upon discharged. No changes will be made to standard hypertensive treatment protocols for either group.

Patients in both groups will be given an appointment to follow-up with their obstetric provider in the office at approximately 14 days postpartum and at about 6 weeks postpartum. The number of measurements *total* and the number of measurements that were *elevated* will be ascertained for each group at this visit.

Patients in both groups will also be prompted to answer two electronic surveys (attached as a separate document to this IRB application) regarding symptoms of preeclampsia, symptoms of volume overload, and breastfeeding continuation at about two weeks postpartum and at the conclusion of the study period. A text message reminder will be sent to patients at the time that each survey is due. A research coordinator will call to obtain responses to the survey questions if patients are unable to complete the survey electronically.

Patients in both groups will be followed from recruitment until six weeks postpartum.

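### Hypotension and volume-depletion symptoms during the home doses have no described structured ascertainment, so a non-significant harm comparison would be weak support for the no-difference hypothesis

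*Combined protocol and SAP*

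**What the plan says.** Section 2.3.1 has the balance of the five-day course dispensed at discharge for the woman to finish at home. It then describes two structured sources of post-discharge data.

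- **Surveys.** There are two, "regarding symptoms of preeclampsia, symptoms of volume overload, and breastfeeding continuation at about two weeks postpartum and at the conclusion of the study period".
- **Home cuff.** Women are asked to measure twice a day with a device "which will transmit blood pressure measurements via Bluetooth from the monitor to the eCC". The stated summary is the count of all readings and the count of those "that were *elevated* will be ascertained for each group at this visit". The blood pressure secondary outcome in section 2.3.6 likewise concerns elevated readings only.

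On harms, section 2.2 (Aim 3, Sub-aim 2) expects "no difference in adverse effects, such as discontinuation of breastfeeding, hypotension, and electrolyte abnormalities". Section 2.10.1 gives a longer list: "Other possible side effects include dryness of mouth, thirst, weakness, lethargy, drowsiness, restlessness, muscle pains or cramps, muscular fatigue, hypotension, oliguria, tachycardia, arrhythmia", and others. Section 2.3.7 lists hypotension, electrolyte abnormalities and renal insufficiency for collection in both groups, with no threshold, source or summary. Under section 2.10.4 women are "instructed to report any concerns about or adverse effects from the study drug", study personnel are to query and record adverse events, and the team looks for adverse events at about 2 and 6 weeks.

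**The concern.** The structured tools ask about what a diuretic should relieve (volume overload, high pressure) but are not described as asking about the mirror image (volume depletion, low pressure). For the doses taken at home, symptomatic harms appear to rest on the woman's own report, on healthcare contacts, or on a general enquiry well after the last dose. Low pressures are stored but have no planned count.

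This matters because the safety hypothesis is one of no difference. Section 2.4.2 tests categorical data with ordinary chi-squared or Fisher tests at p < 0.05, and no margin is set. Events missed in both arms shrink the observed difference and make a non-significant result more likely. Such a result could then be read as confirming the hypothesis. Section 2.4.3 adds that women now go home earlier than before the pandemic, which moves more doses out of hospital.

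**Working it through.** **1. The plan's own figure.** The documents give no power for harms. The 41 per arm comes from the primary outcome: difference 5 mm Hg, SD 6.4, power 90%, 5% significance (taken as two-sided), 10% losses. A two-sample t-test calculation gives 36 per arm, and 36 / 0.90 = 40. That is close to the stated 41, so 41 is used below. After 10% losses, 41 × 0.90 ≈ 37 are evaluable.

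**2. Doses taken at home.** The first dose is given at t0, at most 8 h after delivery, and later doses at t0 + 24k h for k = 1 to 4. Before 48, 72 and 96 h, 2, 3 and 4 doses have been given. That leaves h = 3, 2 and 1 at home. Discharge times are assumptions.

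**3. Delay to the first scheduled enquiry.** The last dose falls no later than 8 + 96 = 104 h, or about day 4.3. The first visit and survey are at about day 14, and 14 − 4.3 ≈ 10 days. The twice-weekly texts come earlier but are described only as reminders.

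**4. Captured event rates.** Assumptions: true symptomatic rates 40% versus 10%, all inpatient events captured, a fraction c of home events captured in both arms, and events spread evenly over the five doses. The captured share is

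f = [(5 − h) + c × h] / 5,

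and the captured rates are 0.40f versus 0.10f. Power is that of the exact two-sided Fisher test at 0.05 with 41 per arm. At full capture it is 0.86.

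| Discharge | h | f (c = 0.5) | Captured rates | Power | f (c = 0.3) | Captured rates | Power |
|---|---|---|---|---|---|---|---|
| 48 h | 3 | 0.70 | 28% vs 7% | 0.65 | 0.58 | 23.2% vs 5.8% | 0.53 |
| 72 h | 2 | 0.80 | 32% vs 8% | 0.74 | 0.72 | 28.8% vs 7.2% | 0.67 |
| 96 h | 1 | 0.90 | 36% vs 9% | 0.81 | 0.86 | 34.4% vs 8.6% | 0.78 |

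**5. How small the trial is for harms anyway.** With 37 evaluable per arm and full capture, power for 40% versus 10% is 0.82, for 30% versus 10% it is 0.49, and for 15% versus 5% it is 0.16. With no events among 37, the one-sided 95% upper limit is 1 − 0.05^(1/37) = 7.8%.

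The event rates and capture fractions have no source in the documents. Step 4 illustrates symptomatic harms. For hypotension the problem differs: readings exist, but nothing says which count as low.

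**The case against.** The plan is not silent on harms.

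- Breastfeeding discontinuation, the first harm named in section 2.2, is surveyed twice and is a secondary outcome.
- Section 2.3.7 commits to collecting hypotension in both groups, and triage or emergency visits and readmissions for any reason.
- Section 2.10.4 makes personnel responsible for querying adverse events through drug intake and again at about 2 and 6 weeks.
- The cuff transmits readings, low ones included. The total and elevated tally serves the elevated-reading outcome and does not prevent other uses of the data.

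All of this stands. A reader might infer that the named harms go uncollected, or that home hypotension is bound to be missed. The documents do not support either: what is lacking is a definition, a planned summary and a described method for the home-dosing days.

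A reader might also conclude that the surveys omit depletion symptoms. Section 2.3.1 calls them "two electronic surveys (attached as a separate document to this IRB application", and that attachment was not available. The text gives topics, not items, so the most that can be said is that such items are not described.

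Third, a reader might see bias built in. The woman, her nurse and her inpatient provider are blinded and both arms follow the same procedures, so losses should be similar by arm. The effect is reduced sensitivity.

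Finally, one could apply 50% or 30% capture to all five doses, which would give power of 0.43 or 0.16 for 40% versus 10%. That ignores inpatient care: nurses give those doses, pressures are taken every six hours, and the team follows pressures and laboratory results.

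**Conclusion.** The point holds as a gap in specification. Breastfeeding and high readings have a described structured method after discharge. Hypotension and volume-depletion symptoms during the home doses do not, and general querying at about day 14 is a weak substitute for symptoms some 10 days old. Under the stated assumptions the cost at 41 per arm is a fall in power from 0.86 to 0.65, 0.74 or 0.81 with 50% home capture, and to 0.53, 0.67 or 0.78 with 30%, for discharge at 48, 72 or 96 h. The loss is small if most doses are given in hospital and material if discharge is early.

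Small numbers and the lack of a margin would make a non-significant harm comparison weak evidence even with complete capture; under-ascertainment weakens it further. The conclusion depends on the unseen survey lacking these items. If it already has them, the symptom part reduces to saying so in section 2.3.1, while the missing definition and summary of hypotension would remain. The primary outcome is unaffected.

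**What to change.** 1. Check the survey attachment. If it lacks them, add a short yes/no checklist of the symptoms in section 2.10.1, identical in both arms. Send it with one of the planned text reminders, timed for the end of the five-day course, and again with the two-week survey. If the items are already there, list them in section 2.3.1.
2. From the transmitted home readings and the inpatient chart, derive for each woman whether she had a low reading during the dosing period, using a cut-off the investigators fix in advance.
3. Report these incidences by arm as risk differences with confidence intervals, and do not treat non-significance as showing no difference.
4. Neither a checklist nor a cuff detects electrolyte abnormalities, and no laboratory schedule is described. Limit that part of Aim 3, Sub-aim 2 to the laboratory values actually obtained, and report how many women in each arm had them.

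The cost is a few survey items, one link in a message already planned, and one derived variable. The downside is a slightly longer survey and more non-specific symptoms in both arms. No dose or clinical rule changes.
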